AF can be paroxysmal or permanent, with varying symptoms (~25% of AF sufferers have no symptoms), ranging from subclinical forms of AF to permanent irregular heart rhythm. Notwithstanding the amount of research produced on AF and its complications, full detail of the pathophysiology linking AF and stroke remains elusive. This knowledge gap results in important drawbacks in clinical practice.

Traditionally, AFRS is predicted using clinical risk scores, e.g., CHA₂DS₂-VASc, which are limited by their modest predictive performance. However, risk factors such as renal impairment, inflammation, atrial remodelling and cardiac and cerebrovascular biomarkers, are not considered in these routine risk scores. Artificial Intelligence (AI) solutions are increasingly used in clinical practice for the prediction and detection of diseases and events, optimisation of treatments, etc. significantly outperforming more traditional techniques based on signal processing [5].

Personalised AI-based prognostication and decision support tools taking account of the patient individual characteristics, and medical and health status history will enhance risk prediction, leading to ultra-early AF identification, guide treatment decisions and prognosticate outcomes. The inclusion of biomarkers related to cardiac damage and automated analysis of ECG characteristics, add further pathophysiological information to the AI modelling. With rapid changes in such biomarkers and vital signs, a dynamic and personalised risk assessment approach taking into account individual pathophysiological risk factors for AF is required to reliably predict outcomes. Currently, risk assessment tools mostly focus on static risk factors and do not account for the dynamic nature of risk, which changes during acute illness, with ageing, and depends on comorbidities.

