- RWMA score, atrial size and volume, left ventricular strain rate, standard echocardiographic measurements as per BSE recommendations
- Change in inflammatory markers white cell count, C-reactive protein and procalcitonin over time

Study Design

This is a single centre mixed methods prospective observational study

Statistics

A detailed statistical analysis plan will be developed for the project in line with the objectives for TARGET to achieve the development and validation of dynamic risk prediction tools and virtual health twins.

Sample size considerations:

The primary aim for this study is to generate data for the development of Health Virtual twins as part of the EU Horizon 2023 TARGET project. We will therefore collect a convenience sample of at 1200 patients with a risk of developing episodes of AF of at least 5%. Given evidence from the literature that subclinical episodes that remain undetected may be as high as 30% or more, we expect that in a cohort of 1200 patients at least 60-120 patients will be diagnosed with episodes of AF of at least 30 seconds.

Although the primary aim of the study is to obtain data for the generation of dynamic risk prediction tools and virtual health twins, we will perform a conventional statistical analysis as part of this work:

The primary outcome (incidence of AF episodes >30 sec in acute illness) will be described as ratio of episodes/patient and as percentage of patients having episodes of AF. We will also analyse time spent in AF a percentage of time monitoring was in place, distribution pattern of AF, duration of AF episodes. Occurrence and frequency of premature atrial complexes as precursors of AF episodes.

We will use conventional logistic regression models to establish the correlation and weight between risk factors for AF (e.g. age, cardiovascular comorbidities, organ dysfunction and support, blood pressure, infection status etc.) and occurrence of AF.

Outcomes will be compared in univariate analyses, using parametric or non-parametric test depending on sample distribution.

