Descriptive statistics will be used to describe demographics, frequency of alerts and blood results in patients with and without episodes of AF. Group comparisons will include parametric (T-Test for independent samples) and non-parametric tests (Mann-Whitney-U-Test), depending on sample distributions. For categorical data, Fisher's exact test will be used to examine associations between variables. Monotonic relationships between two numerical variables will be defined using Spearman's rank correlation coefficient.

Where applicable, univariate analysis will be followed by multivariate logistic regression analysis to identify risk factors for the development of AF episodes postoperatively. Cochran–Mantel–Haenszel test (CMH) will be used for the analysis of stratified categorical data, using occurrence of AF >30 seconds as the binary outcome.

Data will be transferred to the data science group at LJMU ([name]) for development and validation of health virtual twins and dynamic risk prediction models in line with the TARGET proposal Work Packages 4 and 5 specific objective (pages 3, SO3 and 34-35, part B of the TARGET proposal): "Development of personalised virtual twin models for dynamic risk prediction of AF and AFRS that consider the patient individual characteristics and medical and health status history. These models are based on novel predisposing factors and will out-perform currently used clinical scores and models." The novel dynamic prediction tools will be compared against conventionally generated logistic regression models.

Sample Size, Selection and Withdrawal of Subjects

Sample size

The primary outcome will be described as ratio of AF episodes/patients. We aim to recruit at least 1200 patients over 40 month with the following characteristics:

- Patients admitted or referred to Critical Care (NOTE-AF ICU)
- Patients admitted to hospital with acute heart failure (NOTE-AF HF)
- Patients admitted to Emergency Services with sepsis or infection (NOTE-AF Sepsis)
- Patients post upper gastrointestinal surgery (NOTE-AF PULSE-GI)
- Patients after surgical vascular interventions (NOTE-AF Vasc)
- Patients with acute respiratory failure (NOTE-AF Resp)
- Patients admitted after acute stroke (NOTE-AF stroke)

We expect to recruit at least 150 patients in each of the above patient groups.

Inclusion criteria for enrolment

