- Data and/or blood samples obtained so far can be used for the research purposes, but no further samples or data will be collected.
- On patient request all data obtained so far will be deleted from the research database in REDCap and all paper documents containing patient data obtained as part of the study will be destroyed. All blood samples obtained will be destroyed.
- The above options will be available on the retrospective consent form.

For patients who were unable to consent for themselves when enrolled in the study, retrospective consent will be sought in written form for them to remain in the study, once they regain capacity (retrospective consent).

Monitoring

Alongside standard care, vital signs will be monitored continuously for seven days after recruitment using the Isansys Lifecare Patient Status Engine (PSE), a CE-marked class 2a medical device, with wireless wearable biosensors recording single-lead continuous ECG, heart rate, heart rate variability, respiratory rate, temperature, oxygen saturation and non-invasive blood pressure, which are displayed on a tablet (Patient Gateway) in real time and securely stored on a server. Alerts can be sent directly to healthcare professionals using authorized mobile devices.

Alternative systems, e. g. Smartcardia platform (SCaAI patch and cloud platform, a CE Class IIa approved system with monitoring of 7-lead ECG, respiration, SpO₂, activity and cloud-based arrhythmia detection, may be used.

Blood sampling

Surplus serum blood samples will be collected on the day of recruitment (day 1), until day7 and within 24h before hospital discharge. Where a blood sample has been requested for clinical reasons, a serum blood sample will be added to the request if not yet included. Pseudonymized samples will be centrifuged, plasma or serum will be aliquoted, frozen and stored at -80°C for subsequent analysis. Serum samples will be transferred to the Liverpool Biobank at regular intervals to be available for future research. Serum samples will be used to determine cardiac biomarkers, including but not limited to troponins and natriuretic peptides and inflammatory markers, including but not limited to cytokines and interleukins. Samples of patients who decline use in future research will remain stored at freezers within the Liverpool University Hospitals NHS Foundation Trust and destroyed after this project has finished. A detailed flow diagram of blood sampling is provided in Appendix I.

Biomarker testing

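### The protocol takes over the aim of out-performing clinical scores and models in current use, but the only comparison it names is with logistic models newly fitted in this study

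*Protocol*

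**What the plan says.** All references are to the protocol.

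- **Statistics, last paragraph.** Data pass to a data science group for model development in line with the TARGET proposal, whose objective is quoted: "These models are based on novel predisposing factors and will out-perform currently used clinical scores and models". The objective covers both AF and AF-related stroke. The next sentence gives the comparison: "The novel dynamic prediction tools will be compared against conventionally generated logistic regression models".
- **Statistics, conventional analysis.** The logistic models are introduced as part of this study's own work: "We will use conventional logistic regression models to establish the correlation and weight between risk factors for AF". The example predictors mix fixed characteristics, such as age, with ones that change during a stay, such as blood pressure, infection and organ support.
- **The Clinical Problem and the Research Need.** CHA2DS2-VASc is named as an example of the scores traditionally used to predict AF-related stroke, "which are limited by their modest predictive performance". On existing tools generally: "Currently, risk assessment tools mostly focus on static risk factors and do not account for the dynamic nature of risk".
- **Monitoring.** The data open to a dynamic tool are extensive: "vital signs will be monitored continuously for seven days after recruitment".
- **Synopsis, statistical methodology.** Mixed-effects models and survival analysis are also listed, with a pointer to the statistical analysis plan.

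**The concern.** The objective and the comparison sit in adjacent sentences and have different reference points. The objective refers to tools clinicians already use. The comparison refers to a regression that does not exist until this study fits it. The regression is a sensible benchmark for a methods question (does the more complex modelling add to a conventional fit?), but it is not a score or model in current use.

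If the plan is followed as written, the report could say that the dynamic tool beat logistic regression, and readers could take that as meeting the TARGET objective. Conversely, a tie with a good study-specific regression could be read as failure even if both are well ahead of current practice. Neither reading would be supported.

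**Working it through.** **1. Plan's own figure.** The only related number is the expected 60-120 patients with AF among 1200. It reproduces: 1200 x 0.05 = 60 and 1200 x 0.10 = 120. The 10% is inferred, since the protocol states only a risk of at least 5%. No performance measure, margin or sample size is given for the model comparison, so there is nothing further to recompute.

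**2. What the comparison can answer.** Let D, L and S be the performance (for example AUC) of the dynamic tool, the study-fitted logistic model and a currently used score, on the same patients. Then

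D - S = (D - L) + (L - S).

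The objective concerns D - S. The protocol provides for D - L. No section provides for L - S, because no existing score is evaluated. So:

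| Result against logistic | What follows for D - S |
|---|---|
| D > L | positive only if L - S is not too negative; not estimated |
| D = L | equals L - S; could be positive, zero or negative |
| D < L | could still be positive if L exceeds S by more |

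**3. Is an existing score used anywhere in the analysis?** CHA2DS2-VASc appears in the background, for AF-related stroke, and not in the analysis text. NEWS2 appears in a WP1 secondary objective about patient differences. SOFA and APACHE II appear in the schedule and the score appendix. None is named as a comparator for the prediction tools, and none of NEWS2, SOFA or APACHE II is presented as a predictor of AF.

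**4. Data cut-off (conditional illustration only).** The protocol does not say up to what time the logistic model may use data. To see what a mismatch could do, take one marker with baseline value x0 and later value x1 = rho x0 + sqrt(1 - rho^2) e, with logit P(AF) = a + 0.8 x1 and an AF rate of 5%. The slope and correlations are assumptions, not document figures. Simulated AUC (400,000 patients), same single-marker ranking throughout:

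| rho | Baseline value | Latest value | Difference |
|---|---|---|---|
| 0.9 | 0.692 | 0.712 | 0.020 |
| 0.7 | 0.652 | 0.712 | 0.060 |
| 0.5 | 0.611 | 0.712 | 0.101 |
| 0.3 | 0.567 | 0.708 | 0.141 |

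At a 10% rate the differences are nearly the same (0.690 against 0.710 at rho 0.9; 0.563 against 0.707 at rho 0.3). If both models see the latest value, the difference is exactly zero. The table shows why the cut-offs should match. It does not show that they differ.

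**The case against.** **The superiority sentence is not a hypothesis of this study.** It is a quoted consortium objective. NOTE-AF's own primary objective is AF incidence and the generation of data for the tools. There is no test, margin or decision rule. This stands and limits the weight of the point. But the protocol says the modelling is in line with that objective and follows it at once with the comparison, so the two should agree.

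**A freshly fitted logistic model may be the harder benchmark.** If so, beating it would imply beating an older score. That is plausible, but it is an assumption about L - S, which depends on the predictors included and on overfitting with 60-120 events. Computing the score settles it.

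**The objective speaks of scores and models.** A conventional regression is therefore less foreign to it than a comparison with scores alone would suggest. True, but a model fitted here is still not one in current use.

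**The analysis plan may add comparators.** It may, and the protocol does not exclude them. That does not repair the pairing the protocol itself states. Held-out data, prediction times and horizon are ordinary content for that plan, and their absence here is not a fault.

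**A stronger reading to resist.** A reader might infer that the logistic model sees only first-day data, so that the tool would win merely by seeing later data. The documents do not support this: no section restricts the logistic model to baseline, several example predictors vary over the stay, and the synopsis lists methods that can handle repeated data. A simulation that gives the benchmark only the first-day value measures that imposed restriction and says nothing about the protocol.

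**Conclusion.** The mismatch between objective and named comparator holds. As written, the plan can show whether the dynamic tools beat logistic models fitted in this study. It cannot show whether they beat any score or model in current use. This rests on reading the conventionally generated models as newly fitted here. That is not stated word for word, but it follows from the description of the conventional analysis in the same section.

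The size cannot be put as a number, because L - S is unknown and the protocol gives no basis for it. The consequence is confined to the out-performance claim: incidence and the descriptive outcomes are untouched. A win from later data alone is a possibility left open, not something the protocol fixes, and the AUC differences of about 0.02 to 0.14 apply only if the cut-offs differ and the assumed marker model holds. The point is worth settling before models are built, so that the comparator is not chosen after results are known.

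**What to change.** In the last paragraph of the Statistics section, do one of the following.

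1. **Add a comparator in current use.** Name at least one existing score or published model, computed from data already collected. For the AF-related stroke part of the objective, CHA2DS2-VASc is the natural candidate because the protocol names it. For AF onset, the sponsor should choose and justify an existing score or model, since the protocol names none for that purpose. Evaluate it on the same patients, prediction times and outcome as the dynamic tool and the logistic model. Report the logistic comparison as a separate question.
2. **Or narrow the wording.** Confine the out-performance statement to the logistic comparison actually made.

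Under either option, add one sentence giving the logistic model the same data cut-off as the dynamic tool. Details can stay in the statistical analysis plan.

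**Cost.** A little more analysis, and possibly a smaller headline gain. Three limits apply. Computing a score assumes that the history and laboratory forms capture its components. Serial re-scoring is restricted by Appendix E, which schedules APACHE II on day 1 and SOFA on days 1-3 only, so a daily re-scored comparator over seven days would need other collected data. The protocol gives no expected number of AF-related strokes, so the precision of that part of the comparison cannot be judged in advance.

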Appendix A: Semi-structured interview guide for health care professionals

Guidelines/Escalation protocol

Q: What do you do if vital signs deviate?

Q: Are there guidelines on specific interventions?

Q: Is there an algorithm for when you should contact a physician or the rapid response team (does it exist in your hospital)?

Q: Are you allowed to deviate from the guidelines?

(Questions for follow-up questions: do you ever deviate from guidelines, are there periods where is more difficult to follow guidelines, are there patients where you don't think its relevant to follow guidelines)

Q: Do you believe that this way of monitoring helps the patients?

Q: do you think patient monitoring could be improved?

The interviewer demonstrates the app for the participant

Q: Do you see any challenges using this app for vital signs monitoring in your WARD?

Q: do you have anything else to add?

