Purpose of clinical study	To determine 
 1. the incidence, the pattern and the recurrence rate of episodes of atrial fibrillation recorded as part of standard clinical care compared to data obtained through extended remote wireless patch-based monitoring for development and validation of health virtual twins and intelligent clinical decision support tools. 2. the occurrence, incidence and character of alerts registered by wCVSM devices and connected applications. 3. the acceptability and usability of post operative continuous real time physiological monitoring according to patients’ and health care professionals’ experiences and views.
Primary objective	To determine the incidence of clinical and subclinical episodes of AF in acutely unwell patients and to generate data for the development and validation of virtual twins and clinical decision support tools.
Secondary objectives	To describe the incidence and character of alerts registered by wireless continuous vital signs monitoring (wCVSM) devices and connected applications (WARD24). To determine patient acceptability and usability for health care professionals of a

	novel remote monitoring device with automated alert function
Number of Subjects	1200 patients of whom 25 participate in both work packages (1 and 2) of the study, and 25 health care professionals who participate in work package 2
Study Design	Single centre mixed methods prospective observational study
Outcomes	
Primary endpoint:
 
 • Occurrence of clinical and subclinical episodes of atrial fibrillation (AF) 
Secondary endpoints:
 
 • ECG characteristics (p-wave duration, amplitude and dispersion, heart rate variability, QTc, incidence of premature atrial complexes) • Serum concentrations of troponin • Echocardiographic markers of atrial function (RWMA score, atrial size and volume, left ventricular strain rate, standard echocardiographic measurements as per BSE recommendations) • Length of stay • Hospital and 90-day Mortality • MAUQ score • Number of AF episodes • Recurrence of AF episodes • Time spent in AF • Time (in hours) wCVSM is attached • Number of cardiovascular alerts • Number of non-cardiovascular alerts • Change in inflammatory markers (white cell count, C-reactive protein and procalcitonin over time)

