In this study we will monitor vital signs with a novel wireless remote monitoring system, determine the incidence of episodes of AF and assess the usability and acceptability of wCVSM in high-risk patients in various acute conditions. We will conduct two work packages to 1. Obtain data for the generation of virtual digital twins and to quantitatively assess the incidence and pattern distribution of episodes of AF and to 2. Explore user acceptability of the monitoring system and experience of health care professionals in questionnaires and semi-structured interviews.

1. WP1: (Monitoring of vital signs to obtain data for virtual twins to predict clinical and subclinical episodes of AF):

The primary objective of this work package is to determine the incidence of clinical and subclinical episodes of AF in acutely unwell patients and to generate data for the development and validation of virtual twins and clinical decision support tools.

Secondary objectives include:

1. To determine the correlation between number of alerts and occurrence of AF
2. To identify differences in age, gender, length of stay, 30-day mortality, hs-cTn levels, RWMA scores and average National Early Warning (NEWS2) scores in acutely unwell patients
3. To determine the pattern and distribution of AF episodes in acutely unwell patients
4. To identify risk factors for the occurrence of AF episodes
5. To describe the occurrence, incidence and character of alerts registered by wCVSM devices and connected applications (WARD 24).

6. To describe the clinical response to non-cardiovascular alerts and cardiovascular alerts

2. WP2:

We will test the acceptability and usability of wCVSM by conducting questionnaires with patients and health care professionals. We will also conduct semi-structured interviews with health care professionals involved in the care of the study patients to explore their experience with the wCVSM system and the connected software and app. We will develop a thorough implementation guide for the software based on these findings.

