Patients admitted to wards where the WARD247 application is being tested, will be asked to participate. Patients will be asked to complete a questionnaire (Appendix C) to explore their experiences with a remote wireless monitoring system. Health care professionals will participate in semi-structured interviews (Appendix A) and complete the mHealth App Usability Questionnaire (MAUQ) for Standalone mHealth Apps Used by Healthcare Providers a standard questionnaire designed by the University of Pittsburgh (Appendix B). The results and data obtained in this work package will be shared with the WARD24/7 international study team as described in a separate data sharing agreement.

Outcomes for this work package include:

- Number of false alerts
- Number of correct alerts
- MAUQ score
- Semi-quantitative assessment of patient acceptability
- Semi-quantitative assessment of acceptability for nursing and healthcare staff
- Time wCVSM is attached

Study Objectives, Design and Statistics

Research questions and objectives

The **primary research objective** is:

To determine the incidence of clinical and subclinical episodes of AF in acutely unwell patients and to generate data for the development and validation of virtual twins and clinical decision support tools.

The **secondary research objective** is:

To determine patient acceptability and usability for health care professionals of a novel remote monitoring device with automated alert function.

Primary outcome:

The incidence of episodes of AF lasting >30 seconds in acutely unwell and postoperative patients recorded as part of standard clinical care through extended remote wireless patch-based monitoring with or without the use of an alert system (Application).

Secondary outcomes:

Work package 1:

- Length of stay
- Hospital readmissions within 90 days
- Hospital and 90-day Mortality
- Recurrence of AF episodes
- Time spent in AF
- Number of AF episodes
- Complications of AF, e. g. stroke, thromboembolic events
- High sensitivity Troponin concentrations in patients with AF episodes
- Echocardiographic changes in patients with AF episodes

Work package 2:

- MAUQ score
- Percentage change of troponin concentrations in patients with and without episodes of AF
- Time (in hours) wCVSM is attached
- Number of cardiovascular alerts

- Number of non-cardiovascular alerts
- Number of alerts reflecting clinical changes
- Number of alerts reflecting artefacts or non-clinical events

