Appendix B: mHealth PP Usability Questionnaire (MAUQ)

University of Pittsburgh

School of Health and Rehabilitation Sciences
Department of Health Information Management

[name]
[name]
[contact]
[contact]
HIM: <http://www.shrs.pitt.edu/him>
SHRS: <http://www.shrs.pitt.edu>

mHealth App Usability Questionnaire (MAUQ) for Standalone mHealth Apps Used by Healthcare Providers

#	Statements	N/A	1	2	3	4	5	6	7
1.	The app was easy to use.		DISAGREE						AGREE
2.	It was easy for me to learn to use the app.		DISAGREE						AGREE
3.	The navigation was consistent when moving between screens.		DISAGREE						AGREE
4.	The interface of the app allowed me to use all the functions (such as entering information, responding to reminders, viewing information) offered by the app.		DISAGREE						AGREE
5.	Whenever I made a mistake using the app, I could recover easily and quickly.		DISAGREE						AGREE
6.	I like the interface of the app.		DISAGREE						AGREE
7.	The information in the app was well organized, so I could easily find the information I needed.		DISAGREE						AGREE
8.	The app adequately acknowledged and provided information to let me know the progress of my action.		DISAGREE						AGREE

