9.	I feel comfortable using this app in social settings.		DISAGREE						AGREE
10.	The amount of time involved in using this app has been fitting for me.		DISAGREE						AGREE
11.	I would use this app again.		DISAGREE						AGREE
12.	Overall, I am satisfied with this app.		DISAGREE						AGREE
13.	The app would be useful for my healthcare practice.		DISAGREE						AGREE

14.	The app improved my access to delivering healthcare services.		DISAGREE         AGREE
15.	The app helped me manage my patients' health effectively.		DISAGREE         AGREE
16.	This app has all the functions and capabilities I expected it to have.		DISAGREE         AGREE
17.	I could use the app even when the Internet connection was poor or not available.		DISAGREE         AGREE

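### The staff interviews are meant to explore experience with the monitoring system and app, but no question in the interview guide asks about the participant's own use of it

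*Protocol*

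**What the plan says.** The synopsis (Number of Subjects) plans for "25 health care professionals who participate in work package 2". The Introduction's description of WP2 says the interviews are held with "health care professionals involved in the care of the study patients to explore their experience with the wCVSM system", together with its software and app, and that the implementation guide for the software will rest on these findings. The secondary research objective includes usability for health care professionals. MAUQ score and a semi-quantitative assessment of staff acceptability are among the WP2 outcomes.

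The same professionals receive both staff instruments, the interview guide in Appendix A and the MAUQ in Appendix B.

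- **Appendix A** opens with what staff do when vital signs deviate, and with guidelines and escalation. It then asks two questions about monitoring. After those, "The interviewer demonstrates the app for the participant". The only question that names the app comes next: "Do you see any challenges using this app for vital signs monitoring in your WARD". A closing open question ends the guide.
- **Appendix B** contains statements such as "Whenever I made a mistake using the app, I could recover easily and quickly" and "The app helped me manage my patients' health effectively".

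**The concern.** The interviews have a stated purpose, and the guide that is to deliver it does not address that purpose. An interviewer who follows Appendix A would learn how the ward escalates abnormal vital signs today and how a colleague reacts to being shown the app. The interviewer would not be prompted to ask what happened when the colleague used it: whether alerts arrived, what was done about them, how many seemed false, and what they did to the workload. The Introduction itself names alarm fatigue and changed nursing routines as the central issues in implementing such a system.

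At stake are the usability part of the secondary objective and the evidence base of the implementation guide. The gap is hard to repair once the interviews are done. A second, smaller issue is that many MAUQ statements assume use, yet nothing in the document records whether a respondent has used the app. A reader of the scores could not tell what experience lies behind them.

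**Working it through.** No arithmetic beyond counting applies, and the protocol gives no calculated figure to reproduce; the 25 professionals are stated without a derivation. The check sets the purpose beside the instruments.

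**Step 1. Appendix A, question by question (paraphrased, in order).**

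| # | Subject | Asks about own use of the app or about alerts? |
|---|---|---|
| 1 | What staff do when vital signs deviate | No, practice |
| 2 | Whether guidelines on interventions exist | No, practice |
| 3 | Whether an algorithm governs calling a physician or rapid response team | No, practice |
| 4 | Whether deviation from guidelines is allowed (with listed follow-ups on the same subject) | No, practice |
| 5 | Whether the way of monitoring helps patients | Ambiguous as to which system; not about use |
| 6 | Whether patient monitoring could be improved | No, general |
| – | Demonstration of the app | – |
| 7 | Challenges seen in using the app on the ward | Names the app, but looks ahead |
| 8 | Anything to add | Open |

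Count: four questions on practice, two on monitoring, one prospective question on the app and one open closing question, 4 + 2 + 1 + 1 = 8. Questions on the participant's own use, alerts received, responses, false alerts or workload: 0 of 8. Question 5 could be taken to mean the new system. It follows four questions on practice and precedes the demonstration, so it cannot be relied on to draw out experience with the app.

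**Step 2. MAUQ.** By my reading, statements 1, 2, 3, 4, 5, 7, 8, 10, 11, 14, 15 and 17 presuppose hands-on use, which is at least 12 of 18.

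**Step 3. Who answers.** The inclusion and exclusion criteria are written for patients. For staff, the only stated restriction is involvement in the care of study patients. WP2 patients are on wards where the application is being tested, so some contact with the system is likely. Involvement in care is still not the same as use of the app: the Monitoring section says alerts can be sent to authorised mobile devices, not that they will be.

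**Step 4. What is recorded about use.** The patient questionnaire (Appendix C) asks for how many days the system was used. Neither staff instrument has a matching item, and the schedule in Appendix E has no row for staff assessments.

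**Result.** The gap in Step 1 needs no assumption about exposure, because it exists even if all 25 are users. Steps 2 to 4 add that MAUQ scores cannot be interpreted by exposure.

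**The case against.** The strongest reply is that the current-practice questions belong in the guide. The Introduction plans to compare monitoring practices across countries after sharing data with the WARD24 pilot, and the Rationale speaks of learning users' perceptions before a device is rolled out. Questions on escalation and on foreseen challenges serve both aims. This stands, and it is why those questions should be kept. It explains what the guide contains but does not supply what is missing for the experience aim.

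A second reply is that a semi-structured interview allows probing and ends with an open question, and that a demonstration can be a shared prompt for people who already use the app. That is fair. However, the only listed follow-ups concern departures from guidelines, so the experience content would depend on the individual interviewer. Counts of true and false alerts are WP2 outcomes, but they do not capture how staff experienced the alerts.

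Third, the separate WARD24 protocol, mentioned as an appendix, is not in this file and might set rules on staff exposure. That possibility remains open. This protocol does not refer to it for that purpose.

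A reader might go further and infer that MAUQ scores will be first impressions of a demonstration, or that the staff outcomes will come from people who never used the system. The documents do not support that. They never say the MAUQ follows the demonstration, every MAUQ item has an N/A box, and the restriction to staff caring for study patients makes some exposure likely. No figure allows the number of non-users among the 25 to be estimated. Nor does it follow that the instruments measure no usability at all: the MAUQ completed by users does measure it.

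**Conclusion.** The point holds as a mismatch between stated purpose and instrument. The protocol promises professionals' experience with the system, software and app. None of the eight main questions in its interview guide asks for it, and the one question naming the app is prospective and follows a demonstration. This rests only on the text of Appendix A and the WP2 description.

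The MAUQ part is weaker. Use is presupposed by many statements but is neither required nor recorded in this document. On its own that would be missing detail; it matters here because the same professionals answer both instruments.

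The reach is limited to a component with 25 staff, a secondary objective and the implementation guide. The primary outcome, the cohort of 1200 patients and the virtual-twin work are not affected. The change is worth making before the first interview because it is cheap and cannot be made afterwards.

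**What to change.** 1. Keep all existing questions in Appendix A, so that comparison with the WARD24 team is preserved.
2. Add questions on the participant's own use of the app, alerts received and how they were responded to, alerts judged false, and effect on workload. Placing them before the demonstration would keep the answers from being shaped by it.
3. Record each professional's amount of app use (for example, number of shifts) before the interview and the MAUQ.
4. Report MAUQ scores for staff who have used the app in the care of a monitored patient separately from those who have only seen the demonstration. Non-users need not be barred, since reasons for not using the app are themselves informative.

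The cost is a revised appendix, a slightly longer interview and one extra recorded item. No additional participants or visits are needed. If the separate WARD24 protocol already sets a rule on staff exposure, a cross-reference to it should be added.
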